	drawn at months 1, 2, 3, 4, 5, 6, 8, 10, 12, 15, 18, 21, and 24. Any medically-indicated interventions will be made at those visits. Subjects will then be consented for a long-term follow-up study with semi-annual to annual visits and lab draws over the subsequent 13 years.
Study Duration	Each patient will be followed for 24 months. There will be a separate study for long-term follow-up for these patients for years 3-13. The total follow-up period for these subjects will be up to 15 years.
Study Agent/Intervention Description	The Investigational New Drug to be tested is autologous BM CD34+ cells transduced ex vivo with a self-inactivating (SIN) HIV-1 based lentiviral vector: EFS-ADA (also referred to as OTL-101). The vector has been produced as cell-free lentiviral supernatant from the 293T cell line, and has an envelope pseudotype from the vesicular stomatitis virus (VSV). The vector will be used for ex vivo transduction of CD34+ progenitor cells from the BM of infants or children with adenosine deaminase (ADA)-deficient severe combined immunodeficiency (SCID). OTL-101 will be subsequently infused intravenously after a single non-myeloablative dosage of busulfan (4 mg/kg intravenously x1).
Primary Objective	The primary objectives are: 
 to examine the safety of autologous transplantation of bone marrow CD34+ cells transduced with the EFS-ADA lentiviral vector (OTL-101). The safety review will include the identification of grade III/IV serious adverse events (SAE). Subjects will also be monitored for clinical toxicities, replication competent lentivirus, and monoclonal expansion at regular intervals by a clinician, as well as standard blood counts and chemistries. to estimate overall and event-free survival by 12 months where failure is defined by one of the following endpoints: death; reinstitution of PEG-ADA; or performance of an allogeneic BMT.

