11.2 Design Considerations and Data

This is a subject-level historically controlled, prospective, non-randomized Phase I/II clinical trial to assess the safety and efficacy of autologous transplantation of CD34+ cells originated from the bone marrow of ADA-SCID infants and children following human ADA cDNA transfer by the EFS-ADA lentiviral vector.

Descriptive results will be presented for the study cohort.

Comparisons will be made to three cohorts:

- 1) A historical control group consisting of ADA-SCID HSCT-treated subjects lacking a medically eligible HLA-matched sibling/family donor and treated at GOSH/UCL (UK) or Duke University Children's Hospital, North Carolina Transplant Center (USA) from the year 2000 onward
- 2) A historical control group consisting of ADA-SCID HSCT-treated subjects having a medically eligible HLA-matched sibling/family donor and treated at GOSH/UCL (UK) or Duke University Children's Hospital, North Carolina Transplant Center (USA) from the year 2000 onward
- 3) All HSCT-treated subjects from GOSH/UCL or Duke University Children's Hospital, who were treated with HSCT from the year 2000 onward, with any type of donor

Details on the historical HSCT control groups from GOSH/UCL and Duke University Children's Hospital can be found in [Appendix H](#).

Statistical analyses will be performed, and their outcomes presented, in three stages:

- Interim look – 6 months
 - Descriptive statistics for all available subjects
- Primary analysis - Comparison on primary efficacy endpoints to the HSCT control cohorts—12 month follow-up analysis
 - Descriptive statistics for the complete study cohort, with all patients having reached at least 12 month follow-up
 - Comparison to HSCT control cohorts on safety, primary efficacy endpoints and need of immunoglobulin replacement (IgRT) (main secondary efficacy endpoint).
- End of study analysis:
 - Descriptive statistics for the complete study cohort, with all patients having completed the study (24-month follow-up)
 - Comparison to HSCT control cohorts on safety, primary efficacy endpoints and need of immunoglobulin Replacement (IgRT) (main secondary efficacy endpoint).

In each study stage and for all analyses, all relevant data available will be used.

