8.2.17 Exposure

Duration of follow-up in months will be calculated for the OTL-101 treated subjects as: 12*(date of final evaluation - date of infusion + 1)/365.25.

For the HSCT controls, the duration of follow-up will be recorded on the eCRF.

Duration of follow-up will be summarized for the OTL-101 treated and the HSCT control groups using descriptive statistics. In addition, the total subject-years of follow-up in each treatment group will be presented.

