8.3.2.2 Use of Immunoglobulin Replacement Therapy

The number (%) of subjects receiving immunoglobulin replacement therapy (IgRT) will be summarised by visit for the OTL-101 treated subjects.

The time to cessation of IgRT will be calculated (in months) as:

12*(stopping date of IgRT – date of transplant) /365.25,

or, for HSCT control subjects for whom the dates were not recorded, as:

age in months when IgRT stopped – age in months at transplant.

Time to cessation of IgRT will be summarised for the OTL-101 treated and HSCT control groups using descriptive statistics and, if appropriate, estimated from a Kaplan-Meier curve in which subjects who are still receiving IgRT will be censored at the time of their last visit.

The number (%) of subjects who have stopped treatment with IgRT at 12, 18 and 24 months without restarting at any subsequent time point will be summarized for the OTL-101 treated and HSCT control groups (data permitting).

In addition, serum immunoglobulin levels (IgG, IgA and IgM) will be measured at each visit for the OTL-101 treated subjects. Levels of IgG, IgA and IgM and changes from baseline will be summarised by visit using descriptive statistics. In addition, plots of the median value and range over time on a logarithmic scale will be produced for each parameter along with individual plots for each subject which will include age-dependent normal ranges provided by the study sites.

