8.3.2.3 Rate of Severe Infections

Infections will be recorded as adverse events. The infections of interest in this study are severe infections or opportunistic infectious episodes, defined as infections requiring hospitalization or prolonging hospitalization and/or documented infections by opportunistic pathogens (e.g. interstitial pneumonia, intractable diarrhoea).

The number (%) of subjects reporting severe infections or opportunistic infectious episodes along with the number of events reported will be summarized for the OTL-101 treated and

Final Version 4.0 Page 19 of 27

HSCT control groups (data permitting). In addition, the infection rate will be calculated as the number of infections/the total follow-up time. The rate will be calculated both within each treatment group and for each individual subject. The subject infection rate will be summarized by treatment group using descriptive statistics. In addition to the rate for the entire follow-up period, the rate will be calculated for both the first 12 months following transplant and for the remaining study period.

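### The descriptive IgRT and severe-infection comparisons with HSCT controls lack a common 24-month window, and the IgRT-cessation analyses have no rule for deaths

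*SAP*

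**What the plan says.** SAP section 6 names IgRT use and infection rate as key secondary endpoints, to be compared with the HSCT cohorts at the primary and end-of-study analyses. Protocol 11.2 ranks IgRT need as the main secondary efficacy endpoint. No test is specified for either comparison.

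The rules are:

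- **IgRT counts (SAP 8.3.2.2).** Both groups, data permitting: subjects who have "stopped treatment with IgRT at 12, 18 and 24 months without restarting at any subsequent time point".
- **IgRT curve (SAP 8.3.2.2).** If appropriate, a "Kaplan-Meier curve in which subjects who are still receiving IgRT will be censored at the time of their last visit". Death is not mentioned.
- **Infections (SAP 8.3.2.3).** "The number (%) of subjects reporting severe infections or opportunistic infectious episodes along with the number of events reported will be summarized" by group, and "the infection rate will be calculated as the number of infections/the total follow-up time". Besides the rate over all follow-up, "the rate will be calculated for both the first 12 months following transplant and for the remaining study period".

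On follow-up, Protocol 1.1 says "Each patient will be followed for 24 months", with later years in a separate study. Controls were transplanted in 2000-2016 (Protocol Appendix H). SAP 8.2.17 says "For the HSCT controls, the duration of follow-up will be recorded on the eCRF", and Protocol 11.2 says "In each study stage and for all analyses, all relevant data available will be used". Appendix H attaches the 1- and 2-year time points to survival and event-free survival only; it gives none for IgRT or infections. The Duke data list records when IgRT was restarted after transplant, with no upper limit.

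**The concern.** The two groups can be observed for different lengths of time, and several summaries depend on that length.

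- **No restart.** At month 24 an OTL-101 subject has no later in-study time in which to restart, so the condition is met automatically. A control observed for longer can still fail it. At end of study the look-ahead from months 12 and 18 is 12 and 6 months for OTL-101, and longer for any control followed beyond month 24.
- **Infections.** A person-time rate corrects for unequal follow-up only if the hazard is constant. The number infected and the event count are not corrected at all. The part of the split after month 12 has no stated end for controls. The first-12-month rate is already on a common window.
- **Deaths.** Nothing says how a death on IgRT enters the curve, or how deaths and unknown status enter the 12-, 18- and 24-month counts. SAP 8.3.1.1 does define unknown status for survival.

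At stake is whether a difference in these key secondary figures reflects treatment, length of observation or mortality.

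**Working it through.** The documents state no rate, power or expected difference for these endpoints, so there is no planned figure to reproduce. The checks below give both groups identical true behaviour and see what the stated rules return.

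**Inputs.** From the documents: OTL-101 follow-up of 2 years; overall survival of 86%, 81%, 66% and 43% by donor type in the multinational HSCT series (Protocol 2.1.3.1 e), so 14, 19, 34 and 57% deaths. That series is not the control cohort. Assumed: control follow-up f of 5 or 8 years, all hazards, and all stopping shares.

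**1. No restart.** The share of those off IgRT at time t who remain counted is exp(-h(f - t)), with restart hazard h.

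| Time | h per year | OTL-101 (f = 2) | Controls, f = 5 | Controls, f = 8 |
|---|---|---|---|---|
| Month 12 | 0.02 / 0.05 / 0.10 | 98 / 95 / 90% | 92 / 82 / 67% | 87 / 70 / 50% |
| Month 24 | 0.02 / 0.05 / 0.10 | 100 / 100 / 100% | 94 / 86 / 74% | 89 / 74 / 55% |

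For example, exp(-0.05 × 3) = 0.86 and exp(-0.05 × 6) = 0.74. With no restarts there is no gap.

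**2. Overall infection rate.** Let y1 be the hazard in year 1 and y2 the hazard after it. Let a share m of controls die evenly over months 0-6. Then

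rate = (y1·PT1 + y2·PT2)/(PT1 + PT2), with PT1 = (1 - m) + 0.25m and PT2 = (1 - m)(f - 1).

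At m = 0.34, PT1 = 0.745, and PT2 = 0.66, 2.64 or 4.62 for f = 2, 5 or 8.

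| y1, y2 | OTL-101 rate | Control rate, f = 5 / 8 | Spurious ratio | Ratio with controls cut at 24 months |
|---|---|---|---|---|
| Constant | same | same | 1.0 | 1.0 |
| 1, 0.5 | 0.75 | 0.610 / 0.569 | 1.23 / 1.32 | 0.98 |
| 1, 0.1 | 0.55 | 0.298 / 0.225 | 1.85 / 2.44 | 0.95 |

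**3. Rate after month 12.** If the hazard is flat after year 1 the ratio is 1.0. If hazards run 1.0, then 0.5 in year 2, then 0.1, OTL-101 shows 0.5. Controls show (0.5 + 3 × 0.1)/4 = 0.200 or (0.5 + 6 × 0.1)/7 = 0.157, a ratio of 2.5 or 3.2. If this period means months 12-24 in both groups, that artefact disappears.

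**4. Percentage infected.** The formula is (1 - m)(1 - exp(-(y1 + y2(f - 1)))) + m(1 - (1 - exp(-0.5y1))/(0.5y1)). With y1 = 1 and y2 = 0.1, OTL-101 shows 67%. Controls show 75-82% with no deaths but 57-61% at m = 0.34, so the direction reverses. Cutting controls at 24 months gives 51% at m = 0.34, which widens the gap from 6-10 points to about 15.

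**5. IgRT curve if deaths on IgRT are censored.** Suppose deaths come first and 60% of survivors then stop. One minus Kaplan-Meier is 60% at any mortality. Alive and off IgRT among all treated is 0.6(1 - m):

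| Deaths | 14% | 19% | 34% | 57% |
|---|---|---|---|---|
| Alive and off IgRT | 52% | 49% | 40% | 26% |
| Gap, points | 8 | 11 | 20 | 34 |

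If death and cessation instead run concurrently over 24 months, take a cessation hazard s = -ln(0.2)/2 and a death hazard d = -ln(OS)/2. One minus Kaplan-Meier is then 80%. The cumulative incidence of stopping, s/(s + d) × (1 - exp(-2(s + d))), is 74, 69 and 60% at survival of 81, 66 and 43%. The size depends on the timing of deaths; the direction does not. With no deaths the gap is zero, as for the 18 evaluable OTL-101 patients in Protocol 2.1.6.2.

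**Scale.** The exact 95% interval for 12 of 20 is 36-81%, so many of these artefacts are smaller than sampling error. Unlike sampling error, they are systematic.

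**The case against.** **Control follow-up is not given.** Transplant dates are not observation times, and the Duke laboratory windows end at 17-30 months. This stands: 5 and 8 years are guesses, and the sizes are illustrative. Those windows do not, however, cap IgRT or infection data.

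**The wording has bounded readings.** The no-restart phrase could mean the later of the listed time points, and the post-month-12 rate could mean months 12-24. Using all relevant data does not forbid a window. These readings are plausible and the plan should state which applies. The overall rate, whose denominator is total follow-up, has no such reading.

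**Censoring of deaths is inferred from silence.** A reader might infer that the SAP instructs this. It does not: a subject who has died is not still receiving IgRT, so the text leaves the case open. Censoring is only the usual Kaplan-Meier default, and the curve is optional. For the counts, the SAP 7.1 population is all treated patients and a death on IgRT is not a stop, so a sensible programmer would come close to alive and off IgRT. Death after stopping and unknown status remain undefined. SAP 10.1 moved some programming detail to documentation not available here, which may settle this.

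**The comparisons are descriptive.** No test or decision rests on them, and SAP 8.2.17 and 8.3.1.1 show follow-up and survival as well. Protocol 11.6.2.4.2 lists infection only among additional secondary endpoints. This lowers the severity but does not supply a window or a death rule.

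**Conclusion.** The point holds as a minor-to-moderate defect in how the key secondary comparisons are specified. The no-restart condition and the all-follow-up infection summaries are uncapped for controls, and IgRT cessation has no death rule.

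A reader might infer that the plan as a whole is tilted towards OTL-101. The documents do not support that, because the directions differ:

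- The no-restart count favours OTL-101 if any restarts occur after month 24.
- The overall infection rate works against OTL-101 if infections fall over time and controls are followed for longer.
- A cessation curve that censors deaths flatters whichever group has more deaths.
- The percentage infected can go either way.

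Each effect vanishes under its own condition: no restarts, a constant hazard, or no deaths. Actual sizes cannot be fixed, because control follow-up, restart and infection hazards and control-cohort mortality are not in the documents. Nor do these gaps reach the primary overall and event-free survival analyses.

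**What to change.** 1. Apply the no-restart condition only up to month 24 in both groups.
2. Report person-time infection rates for months 0-12, 12-24 and 0-24 in both groups, truncating controls at 24 months. Base the comparison on the 0-12 and 12-24 rates.
3. Keep the number (%) infected as supportive, with mortality beside it. A cap removes its dependence on follow-up but not on mortality.
4. Report the proportion alive and off IgRT at 12, 18 and 24 months among all treated subjects. Count deaths as not off IgRT and show unknown status separately, as in SAP 8.3.1.1.
5. If a cessation curve is shown, use cumulative incidence with death as a competing event and keep Kaplan-Meier as supportive.

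The cost is SAP wording and standard SAS code. Control data beyond 24 months become supportive only. Restart and infection timing is needed for controls. The Duke list already covers IgRT restarts. The GOSH list in Appendix H mentions only prior or current immunoglobulin use, so restart dates there need confirming from the medical records already planned for access.

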6.5 Prophylactic Medications and Procedures

Prophylactic medications:

Subjects will receive acetaminophen and diphenhydramine prior to the infusion of OTL-101.

As a part of standard care for autologous hematopoietic stem cell transplantation, patients will be provided coverage for *Pneumocystis jirovecii* and mucosal yeast infection until adequate immune reconstitution has occurred (see [Section 7.4](#)). Medications may include trimethoprim/sulfamethoxazole, pentamidine, atovaquone, or other effective PJP prophylaxis started by Day + 30 after cell product infusion and p.o. fluconazole or nystatin for mucosal thrush prophylaxis. Prophylactic anti-viral medications (e.g. acyclovir) may be given for clinical care considerations, but are not required in the absence of evidence of infection or exposure to herpes or other viruses.

Seizures are a rare, but known side effect of busulfan. To prevent this occurrence, we will prophylactically treat our subjects with oral or intravenous Keppra prior to starting busulfan until at least 24 hours after completion. Nausea and vomiting are other side effects of busulfan chemotherapy. Subjects will receive oral or intravenous Ondansetron prior to starting busulfan to prevent nausea and vomiting.

Standard treatment for patients with SCID includes regular immunoglobulin administered either subcutaneously or intravenously. We will continue this through the process. Patients will not receive any other prophylactic medications unless clinically warranted.

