7 STUDY PROCEDURES/EVALUATIONS

7.1 OVERALL STUDY PLAN

These studies will seek to determine the safety (as primary end-point) and efficacy (as secondary end-points) of transplantation of OTL-101 to provide functional immunity without exogenous enzyme replacement therapy. Overall, the study procedures are within one of four distinct phases:

1. Pre-treatment
2. Treatment
3. Post-treatment
4. Extended Follow-up

The following is a brief overview of the Study Plan. The detailed study plan is described in [Appendix B: Schedule of Procedures/Evaluations](#)

7.2 Pre-treatment phase:

Baseline Screening: The first part of the study will involve performing laboratory tests to determine whether the subject meets the inclusion criteria and does not have a contra-indication causing exclusion.

Continuation/Cessation of Medications/Procedures: If enrolled into this study and meeting all eligibility criteria, the subject will continue PEG-ADA ERT and prophylactic intravenous or subcutaneous immunoglobulin replacement. Trimethoprim/sulfamethoxazole, if being given, will be stopped 5-10 days prior to bone marrow harvest.

Central venous access: If the subject does not already have a central venous access device, a central venous access device will be placed for ease of phlebotomy and bone marrow cells and drug administration. The decision between percutaneous intravenous central catheter (PICC) line, a tunneled central venous catheter, or an implanted sub-cutaneous access device will be made by discussions with parents and line placement surgeon. A PICC line may instead be placed as a separate procedure with appropriate sedation or a central venous line may be placed during the general anesthesia for the bone marrow harvest.

7.3 Treatment Phase:

Bone marrow harvest: Bone marrow harvest will be under general anesthesia to ≤ 20 ml/kg.

For patients older than 2 years of age, where our experience indicates that the yield of bone marrow CD34+ cells is lower than in younger children, the patient may be asked to have a “back-up” bone marrow harvest performed approximately 1-3 months prior to the actual gene transfer procedure. The back-up must contain $\geq 5 \times 10^7$ nucleated cells/kg from whole bone marrow or 3×10^7 mononuclear cells from ficolled marrow. Marrow mononuclear cells will be cryopreserved and kept as the back-up.

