a) *Pneumocystis jirovecii* prophylaxis (PJP): Trimethoprim/sulfamethoxazole (TMP/SMX) will be stopped prior to marrow harvest and an alternative PJP prophylaxis regimen will be used at least until ANC >500 for three consecutive measurements, when TMP/SMX may be resumed. Suitable alternative PJP prophylaxis medications include pentamidine (intravenous or aerosolized) or atovaquone. Dapsone should be used with caution, due to its potential myelosuppressive effects. PCP prophylaxis may be stopped when CD4 $>200/\mu\text{l}$ and PHA response is $>50\%$ lower limit of lab normal response range ([Griffith, 2009](#)).

b) Patients will be given a prophylactic antifungal medication, such as oral nystatin or fluconazole in standard doses. This may be stopped when CD3 $>200/\mu\text{l}$.

Additional or alternative antibiotics may be administered based on clinical care considerations (these will be recorded as Concomitant Medications).

Intravenous (or SQ) gamma-globulin will be administered at standard dosage and frequency (e.g. 400-600 mg/kg q3-4 weeks). Indications for considering stopping immunoglobulin replacement include: absolute CD4 $>200/\mu\text{L}$, absolute B cell $>100/\mu\text{L}$, IgA or IgM $> \text{LLN}$ for age. Immunoglobulin replacement may be continued based on clinical care considerations.

7.5 Extended Follow-up Phase:

Research Evaluations: After the infusion of the final cell product, follow-up studies will determine whether gene-modified cells have engrafted and are able to produce mature lymphoid and hematopoietic cells containing and expressing the ADA gene and the extent and time-course of immune reconstitution. Serial samples of peripheral blood will be analyzed for the frequency of cells containing the inserted ADA vector over a two year follow-up phase.

Stable persistence of immune function in the absence of PEG-ADA treatment will constitute evidence that the gene transfer has led to clinically beneficial effects on immune function. The Phase I/II study will also attempt to determine whether the presence of mature lymphoid cells will contain and express the EFS-ADA vector in greater frequency than the subjects in the prior γ -retroviral vector trials and if those cells will contribute to more rapid or robust immune function.

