8.2 Enrollment/Baseline

If subjects meet inclusion criteria and have no findings causing exclusion, then subjects will be enrolled.

Physical exam, specified blood tests, and urinalysis will be performed within 3 days of the bone marrow harvest procedure. These studies must meet the inclusion criteria to allow enrolled subjects to undergo the bone marrow harvest. Determinations of ADA enzymatic activity, erythrocyte deoxyadenosine nucleotide levels, and immune function will be performed after screening and before treatment. PBMCs and serum will be collected and banked for future RCL determination.

1. Complete physical examination including recording of height (cm), weight (kg), and vital signs (temperature, pulse rate, respiratory rate and blood pressure).
2. Blood tests:
 - a) Comprehensive metabolic panel (albumin, AST/ALT, alkaline phosphatase, total protein, total bilirubin, creatinine, BUN, glucose, calcium, Na⁺, K⁺, Cl⁻, CO₂)
 - b) Magnesium, phosphate

- c) CBC with differential and platelet count
- d) INR or PT/PTT
- e) Type and cross for 2 units PRBC
- f) Pregnancy test, if female of child-bearing age

3. Urinalysis: routine urine chemistry and microscopic examination.

The following labs must be done prior to infusion of OTL-101:

[figure not shown]
- 4. Measurements of leukocyte or erythrocyte ADA enzymatic activity and erythrocyte deoxyadenosine nucleotide levels
- 5. Measurement of immune function
 - a. Determination of absolute numbers of CD3, CD4 and CD8 T lymphocytes, CD19 B lymphocytes and CD56/CD16 NK cells.
 - b. Proliferative responses to PHA, Tetanus toxoid and *Candida*
 - c. Measurement of serum immunoglobulin levels (IgG, IgA, IgM)
 - d. Measurement of specific antibodies to tetanus, polyribosylphosphate (PRP)
- 6. PBMC and serum banking for RCL determination

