8.3.2.10 Antibody Responses

Antibody responses to Tetanus and Polyribosylphosphate (PRP) were evaluated.

Final Version 4.0 Page 21 of 27

The response to each of the antibodies will be summarized for the OTL-101 treated subjects using descriptive statistics.

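### SAP 8.3.2.2 summarises IgG and its change from baseline without regard to immunoglobulin replacement, so neither can be read as the subjects' own IgG production

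*SAP*

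**What the plan says.** SAP 8.3.2.2 provides that "serum immunoglobulin levels (IgG, IgA and IgM) will be measured at each visit for the OTL-101 treated subjects", and then: "Levels of IgG, IgA and IgM and changes from baseline will be summarised by visit using descriptive statistics". It adds plots of the median and range over time, and individual plots against age-dependent normal ranges. None of this depends on IgRT status. The same section separately tabulates the number on IgRT by visit, time to IgRT cessation, and the number who have stopped at 12, 18 and 24 months without restarting.

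The protocol keeps replacement going throughout:
- Before treatment (7.2): "the subject will continue PEG-ADA ERT and prophylactic intravenous or subcutaneous immunoglobulin replacement".
- During treatment (6.5): "Standard treatment for patients with SCID includes regular immunoglobulin administered either subcutaneously or intravenously. We will continue this through the process".
- After infusion (7.4): "Intravenous (or SQ) gamma-globulin will be administered at standard dosage and frequency", with 400 to 600 mg/kg every 3 to 4 weeks as the example. The indications for considering a stop are CD4 count, B-cell count, and IgA or IgM. IgG is not among them.

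For specific antibodies, SAP 8.3.2.10 says: "The response to each of the antibodies will be summarized for the OTL-101 treated subjects using descriptive statistics". It names no time point and no condition on immunoglobulin or vaccination.

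**The concern.** Protocol 4.2.2 lists immunoglobulins by class (endpoint 8) and specific antibody responses (endpoint 9) among the assays intended as a laboratory assessment of immune function after gene transfer. A reader will take a by-visit IgG table, with change from baseline, as evidence about the subjects' own antibody production. If the sample contains infused IgG, the table does not show that.

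The change from baseline is the more serious part. Its error does not disappear when IgRT stops, because the baseline value was still taken on replacement. It can point the wrong way for exactly the subjects in whom treatment worked.

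**Working it through.** The documents give no figure to reproduce. The check is a short piece of algebra and a comparison of the collection rules.

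**What measured IgG contains.** Let E(t) be a subject's own IgG at time t and P(t) the infused IgG.

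- Measured value: M(t) = E(t) + P(t).
- Change from baseline: M(t) − M(0) = [E(t) − E(0)] + [P(t) − P(0)].

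Case 1, no own production and IgRT continued: E = 0 throughout, so M(t) = P(t). The subject plots in the normal range whenever the replacement dose achieves that. Under steady dosing the change is about zero.

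Case 2, reconstituted, IgRT stopped and infused IgG cleared: P(t) = 0, so the change is [E(t) − E(0)] − P(0). It is negative whenever the gain in own IgG is smaller than P(0), although own production has risen.

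**What the pooled table shows.** If a fraction p(t) of subjects is on IgRT at visit t, the visit mean is p(t) × mean(on) + [1 − p(t)] × mean(off). The SAP reports p(t) in a separate table but neither component mean. Movement between visits therefore mixes changes in own IgG with changes in p(t). The documents give no values of p(t), so its range is 0 to 1. Protocol 2.1.6.2 says that all UCLA patients with sufficient follow-up had stopped IgRT by the last cut-off, so p(t) may be small at late visits.

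**When immunoglobulins are measured.** The documents disagree.

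| Place | Immunoglobulin levels | Tetanus/PRP antibodies |
|---|---|---|
| Protocol 8.2 (baseline) | no condition | no condition |
| Protocol 7.6.1 | no condition | about every 3 months if off IVIg |
| Protocol 8.4 | every 3 months if off IVIg | no condition |
| Protocol Appendix B (post-treatment list) | no condition | every 3 months if off IVIg |
| SAP Section 3, footnote b | no condition | every 3 months if off IVIg |
| SAP 8.3.2.2 / 8.3.2.10 | each visit, no condition | no condition |

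Protocol 8.4 attaches the condition to the other test. If 8.4 were followed literally, follow-up IgG would be taken off IVIg while the baseline stayed unrestricted. Every change from baseline in a subject on IgRT at entry would then be an off-treatment value minus an on-treatment value, which is Case 2. The change is thus unreadable under either rule.

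**Titres.** Protocol 4.2.2 makes the vaccine-antigen titres conditional on vaccination. Appendix B starts tetanus immunisation at least one year after transplant, with three doses two months apart: 12 + 2 × 2 = month 16 at the earliest for a complete series. A baseline titre is therefore not a response to trial immunisation, yet nothing in SAP 8.3.2.10 excludes it.

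**The case against.** The strongest defence is that IgG sits in a section about IgRT use, beside tables of that use. It is descriptive only, with no test, model or HSCT comparison, and SAP 8.3.2.4 assesses immune reconstitution by lymphocyte subsets. All of that is true and limits the importance of the point. It does not cure it. A marginal count of subjects on IgRT does not show which IgG values were taken on treatment, and cell counts do not show antibody production.

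Four stronger readings are tempting, and the documents do not support them:

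- That tetanus and PRP titres are summarised for everyone while on donor immunoglobulin. The SAP's own schedule (Section 3, footnote b) ties follow-up titres to not receiving IVIg, as do Protocol 7.6.1 and Appendix B. SAP 10.1 records that by-visit titre summaries were removed. What remains is that 8.3.2.10 does not restate the condition, that baseline samples and Protocol 8.4 carry none, and that the condition names only IVIg although subcutaneous replacement is allowed.
- That IgG is mostly infused antibody over the whole 24 months. This cannot be quantified, and use appears to fall. Nor is it established that every subject enters on IgRT: Protocol 11.6.2.2 records previous or current use as a baseline characteristic.
- That every titre before month 16 is passive. Vaccination before enrolment is not ruled out, and the Appendix B schedule names no PRP vaccine, so the month-16 arithmetic applies to tetanus only.
- That IgG should be shown only after a fixed washout, such as 3 months. The documents give no basis for an interval. Restricting to off-IgRT subjects would also show only those who met the stopping indications.

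**Conclusion.** The point holds for IgG. As planned, IgG by visit cannot be read as own production for subjects on IgRT, and change from an on-IgRT baseline can fall in a subject who has reconstituted. This assumes only that infused IgG contributes to measured serum IgG and that subjects on replacement at entry continue it as the protocol states. The proportion of values affected is unknown. IgA and IgM are not in question; the protocol itself uses them when a stop of IgRT is considered.

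For tetanus and PRP the gap is minor: conditions that exist elsewhere in the documents are missing from the analysis text. The safety endpoint and overall and event-free survival are not affected.

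**What to change.** In SAP 8.3.2.2:
- Present IgG by visit split into on and off IgRT, with n in each. Show both groups, because the off group is selected for meeting stopping indications.
- Mark the IgRT stop date, and any restart, on the individual IgG plots. Carry-over soon after stopping can then be seen without imposing an interval.
- Do not present IgG change from an on-IgRT baseline as an efficacy result.
- Keep IgA and IgM for all subjects at all visits.

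Reconcile Protocol 8.4 with Protocol 7.6.1, Appendix B, SAP Section 3 and SAP 8.3.2.2 on which test carries the off-IVIg condition.

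Minor: in SAP 8.3.2.10, state which sample enters the summary, and carry over the off-immunoglobulin condition (intravenous or subcutaneous) and the vaccination condition from Protocol 4.2.2. Unrestricted baseline titres are then not pooled as responses.

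The cost is wording and programming. IgRT use by visit and stop dates are already planned, so no new data are needed. The price is smaller counts: 20 treated subjects (SAP Section 2) are divided between two groups at each visit.
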